6.2 Power and Sample Size

As described in Section 3.11 of the study protocol, power calculations were performed based on the primary effectiveness analysis, which tests whether the fraction of treatment responders is significantly greater than 0.40 (H₀: $\pi \le 0.40$ vs. H_A: $\pi > 0.40$) using a one-sided exact binomial test, based on significance $\alpha = 0.025$ and power $1 - \beta = 0.90$.

Based on the LIFE study, we anticipate an 85.6% success rate among study completers and conservatively estimate 21.3% dropout within 3 months, resulting in an estimated 67% response rate in this study. With as few as 40 subjects in the ITT cohort, the study has ≥90% power to detect a response rate greater than 40%.

Telephone follow-up calls are required in between each Treatment Visit.

⁺ If clean catch urine test is positive, the test must be repeated until either it, or a urine culture test, is negative before performing a Fitting Visit (Visit 2)

[†] If clinically indicated.

[‡] AEs recorded starting at the first Fitting Visit (Visit 2); Con Meds recorded at baseline and reviewed / updated at every visit.

^{††} A pelvic exam and Device Satisfaction questionnaire are required at all early study exit visits after the first Fitting Visit (Visit 2).

Additional subjects, up to the maximum of 150 subjects, will be enrolled through a specified end date in order to provide a more robust analysis.

Withdrawal from the study during the Screening Period is estimated to be substantial due to the baseline diary completion and device fitting requirements. Subjects who are successfully fit with the Eclipse System and successfully complete the Screening Period will be eligible for treatment. Therefore, an estimated 160 to 600 subjects may be recruited into this study in order to achieve 40 to 150 subjects who successfully enter the Treatment Period.

We estimate the subject dropout rate between the start of the Treatment Period and the 12 month visit to be 33%, yielding approximately 25 to 100 subjects completing 12 months of study participation. In a 12-month study of non-surgical management of stress urinary incontinence the dropout rate over this same time period was approximately 36%.¹

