6.3 Randomization Procedure

This is a single-arm, open-label study in which subjects serve as their own controls. No randomization was performed.

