8 STATISTICAL ANALYSIS

8.1 General Considerations

Continuous data will be summarized using count (n) the number of non-missing values and mean, median, standard deviation, minimum and maximum as appropriate. The interquartile range (IQR) may also be reported as appropriate. Categorical data will be summarized using counts and frequencies. In general, means and medians will be presented to 1 more decimal place than collected, and standard deviations to 2 more decimal places. Where appropriate, p values will be presented to 4 decimal places.

A one-sided, 2.5% significance level will be used for the primary efficacy endpoint. All p-values, aside from those in the primary efficacy endpoint, are presented for descriptive purposes only. No adjustments will be made for multiple comparisons.

Recorded data may be presented in data listings, aside from cost utilization data which is evaluated under a separate analysis plan. If listed, enrolled subjects will be listed first, followed by screen failures, where appropriate.

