11.2.3 FIQOL

The FIQOL is administered at Baseline and at 3, 6, 9, and 12 months. The following scoring algorithm is used to create subscale scores for Lifestyle (10 items), Coping/Behavior (9 items), Depression/Self Perception (7 items) and Embarrassment (3 items). Raw item scores are on a 5 point scale for Question 1 (1=Excellent to 5=Poor), 4 point scale for Questions 2a-2m (1=Most of the Time to 4=None of the Time), 4 point scale for Questions 3a-3n (1=Strongly Agree to 4=Strongly Disagree), and 6 point scale for Question 4 (1=Extremely So to 6=Not at All).

- Lifestyle is the average score for questions 2a, 2b, 2c, 2d, 2e, 2g, 2h, 3b, 3l, and 3m, where no more than 4 items are missing
- Coping/Behavior is the average score for questions 2f, 2i, 2j, 2k, 2m, 3c, 3h, 3j, and 3n, where no more than 4 items are missing
- Depression/Self Perception is the average score, where no more than 2 items are missing, of:
 - Question 1 (reverse coded to 5=Excellent to 1=Poor),

- Questions 3d, 3f, 3g, 3i, 3k
- Question 4, multiplied by 0.67 to rescale it to a 4-point range
- Embarrassment is the average score for questions 2l, 3a, and 3e, where no more than 1 item is missing

Subscale scores and their percent changes from baseline will be summarized by visit, based on the PP population.

Changes from baseline in subscale scores will be analyzed separately for each subscale score using a repeated measures model with baseline subscale score as a covariate. Least squares means and associated p-values may be presented for each timepoint during the Treatment Period.

All raw item scores may be listed by subject and visit. Subscale scores and their changes from baseline may be listed separately by subject and visit.

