11.2.4 St. Mark's (Vaizey) Incontinence Severity Score

The St. Mark's (Vaizey) Incontinence Severity questionnaire assesses seven aspects of incontinence severity (solid stool incontinence, liquid stool incontinence, gas incontinence, lifestyle alteration, the need to wear a pad or plug, taking constipating medicines, and lack of ability to defer defecation for 15 minutes).

An overall incontinence severity score, calculated and entered on the CRF, is derived as follows:

- The first 4 questions are scored on a 5-point scale, where 0=Never and 4=Daily
- The next 2 questions (wearing a pad or plug and taking constipating medicines) are scored where 0=No and 2=Yes
- The last question (deferring defecation) is scored where 0=No and 4=Yes
- The item scores are summed to create an overall score on a 24-point scale, where 0 is perfect continence and 24 is total incontinence.
- If any of the items used to create the overall score are missing, the score will be missing. (A missing FI bother item result will not affect the overall score).

An FI bother scale is also administered as part of this assessment. The amount that a subject's bowel control symptoms bothers her on the visit day is ranked on a 4-point scale, where 0=Not at all and 3=Greatly.

The severity score results, changes from baseline and/or percent changes from baseline may be summarized by visit. Changes from baseline in the severity score

will be analyzed using a repeated measures model with baseline severity score as a covariate. Least squares means and associated p-values may be presented for each timepoint during the Treatment Period.

The FI bother scale may be summarized by visit using the PP population. The change from baseline in the FI bother scale, which could take on values of -3 to 3 may also be summarized (continuously) and evaluated using the Wilcoxon Signed Rank test to determine if the average score is significantly different from zero (i.e., no change). The percent change from baseline in FI bother may be summarized as less bothersome (values <0), no change (0), or more bothersome (values >0) by visit.

The individual item scores, overall severity score, and FI bother scale may be listed by subject and visit.

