11.3 Additional Analyses of Diary Data

11.3.1 FI Episodes

The average number of FI episodes per week for each subject may be summarized by diary period (Baseline, Test, 3 month, 6 month, 12 month). The change from baseline and percent change from baseline may also be summarized for each Treatment Diary (3 month, 6 month, 12 month).

Percent changes from baseline will be analyzed using a repeated measures model with baseline average number of weekly episodes as a covariate. Least squares means and associated p-values will be presented for each timepoint during the Treatment Period.

The percent change from baseline in FI episodes will be further categorized by degree of improvement (<50% reduction, >= 50% reduction, >75% reduction, and 100% reduction) and the percent of subjects in each category summarized for each Treatment Diary. These analyses will be based on the PP population.

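### Baseline-adjusted LS means in a single arm: read as tests of zero mean change, their model standard errors omit sampling variation in baseline, so SEs and p-values are generally too small

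*SAP*

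**What the plan says.** SAP 6.3 describes the design: "This is a single-arm, open-label study in which subjects serve as their own controls". Three sections then use the same type of model.

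- **SAP 11.2.3, FIQOL subscales.** Change from baseline is analysed "using a repeated measures model with baseline subscale score as a covariate". On output: "Least squares means and associated p-values may be presented for each timepoint during the Treatment Period".
- **SAP 11.2.4, St. Mark's score.** Change "will be analyzed using a repeated measures model with baseline severity score as a covariate". LS means and p-values are again optional.
- **SAP 11.3.1, weekly FI episodes.** "Percent changes from baseline will be analyzed using a repeated measures model with baseline average number of weekly episodes as a covariate". Here the LS means and p-values are to be presented, not merely permitted.

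None of the three sections states the null value, the baseline value at which the LS means are taken, the covariance structure or how the SE is obtained. None plans a confidence interval; the interval the SAP names for efficacy is the Clopper-Pearson interval for the response rate (11.1). On the status of the results, SAP 8.1 says: "All p-values, aside from those in the primary efficacy endpoint, are presented for descriptive purposes only". Protocol 3.5 lists the change from baseline in mean FIQOL and St. Mark's scores as a secondary endpoint.

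**The concern.** In a randomised comparison, baseline-adjusted LS means are subtracted between arms at a common baseline value, and the sampling error of the overall baseline mean cancels. Here nothing is subtracted. The LS mean change is itself the result, taken by default at the sample's own mean baseline.

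With complete data that LS mean equals the raw mean change. Its model SE, however, uses only the variance left after change has been regressed on baseline. The part of the variance of change that is carried by baseline is left out, although another sample of women would have a different baseline mean and so a different mean change.

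What is at stake is the stated precision of the protocol's secondary symptom and quality-of-life results, and of the weekly-episode analysis. A larger sample does not help, because the model SE and the true SE shrink at the same rate.

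**Working it through.** **The plan's own figure.** The only power statement concerns the primary test: "With as few as 40 subjects in the ITT cohort, the study has ≥90% power to detect a response rate greater than 40" per cent (SAP 6.2). With n = 40, a null rate of 0.40 and one-sided alpha 0.025, the exact binomial test rejects at 23 or more responders. Its actual alpha is 0.0189, and its power at a 67% response rate is 0.924. The statement reproduces, and it does not depend on the models discussed here. The documents give no SD, SE or power for FIQOL or St. Mark's.

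**Inputs.** From the SAP: one arm, change as outcome, baseline as covariate, p-value per visit. Assumed, because the documents give no values: the correlation rho between baseline and follow-up, the ratio k = follow-up SD / baseline SD, a null of zero mean change, and a two-sided 5% level (the SAP sets a level only for the primary endpoint).

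**Formula.** Write D = Y − B for change, with baseline SD 1 and follow-up SD k.

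- Slope of D on B: b = rho·k − 1.
- Residual variance, which the model SE uses: k²(1 − rho²).
- Variance of D, which drives the true SE of a mean change: residual variance + b² = 1 + k² − 2·rho·k.
- Ratio of model SE to true SE: k·√(1 − rho²) / √(1 + k² − 2·rho·k) = √(1 − corr(D,B)²). With k = 1 this is √((1 + rho)/2).
- Actual two-sided error of a nominal 5% test: 2·[1 − Φ(1.96 × ratio)].

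**One case in full.** For k = 1 and rho = 0.5, the residual variance is 1 − 0.25 = 0.75, b² = 0.25 and Var(D) = 1.00. The ratio is √0.75 = 0.866. The actual error is 2·[1 − Φ(1.697)] = 0.090.

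**Range.**

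| k | rho | SE ratio | Actual error at nominal 5% |
|---|---|---|---|
| 1.0 | 0.3 | 0.81 | 11.4% |
| 1.0 | 0.5 | 0.87 | 9.0% |
| 1.0 | 0.7 | 0.92 | 7.1% |
| 1.0 | 0.9 | 0.97 | 5.6% |
| 0.8 | 0.3 | 0.71 | 16.5% |
| 0.8 | 0.5 | 0.76 | 13.8% |
| 0.8 | 0.8 | 0.80 | 11.7% |
| 1.25 | 0.3 | 0.89 | 8.3% |
| 1.25 | 0.5 | 0.94 | 6.4% |
| 1.25 | 0.8 | 1.00 | 5.0% |

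The understatement is zero when rho·k = 1, because b is then zero.

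**Simulation, complete data, k = 1.** With n = 27, 40 and 100 and four follow-up visits, the baseline-adjusted test rejected in 11.0–11.6% (rho 0.3), 8.0–9.2% (rho 0.5) and 6.4–7.4% (rho 0.7), with no improvement as n grew. The unadjusted paired change rejected in 4.4–5.5% across all runs. A fitted mixed model (n = 100, rho 0.5, 400 runs) gave a mean SE of 0.086 against an actual SD of 0.101, and rejected in 9%.

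**The remedy, checked the same way** (n = 60, three follow-up visits, 400 runs):

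| rho | SE, baseline as covariate | SE, baseline as outcome | Actual SD | Rejection, covariate | Rejection, outcome |
|---|---|---|---|---|---|
| 0.3 | 0.123 | 0.153 | 0.155 | 14% | 5.0% |
| 0.5 | 0.112 | 0.129 | 0.134 | 10% | 6.8% |

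For the percent-change model in 11.3.1 the same ratio applies, with the correlation between percent change and baseline in place of corr(D,B). The documents give no basis for a value, so no size is given.

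**The case against.** **The null and the target are not written.** This stands. Conditioning on observed covariates is ordinary regression inference, and the SE is valid if the target is the mean change for women with these baselines. But the SAP does not say it intends that, and the protocol endpoint is the mean change itself. The neighbouring tests point to a no-change null: SAP 11.2.4 tests FI bother against zero, and 11.2.2 tests PGI-I against its no-change score.

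**Nothing is decided on these p-values.** This also stands. They are optional for FIQOL and St. Mark's, descriptive throughout, and mandatory only in the additional episode analysis. Strong results would survive: a reported p of 0.001 becomes about 0.004 at a ratio of 0.87 and about 0.02 at 0.71. At 0.87, only a reported p between about 0.024 and 0.05 would cross 0.05 after correction. A descriptive p-value still needs an SE that matches its target.

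**Stronger readings that the documents do not support.**

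- A reader might infer that the confidence intervals for FIQOL and St. Mark's are too narrow. None is planned; intervals would be affected only if added from these models.
- A reader might infer that precision is overstated at every visit. That depends on rho and k, which are unknown, and the effect can be nil.
- A reader might infer that the trial's main conclusion is at risk. The primary analysis is an exact binomial test that uses none of these models.

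**Small numbers.** An unstructured covariance over five occasions has 5 × 6 / 2 = 15 parameters, while SAP 6.2 foresees as few as about 25 women completing 12 months. This is a fair caution, and the fix needs a fallback.

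**Conclusion.** The point holds in a limited form. For the unconditional mean change from baseline, tested against zero, the SEs and p-values from the models in SAP 11.2.3, 11.2.4 and 11.3.1 are generally too small, because one arm offers no contrast in which baseline variation cancels.

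With equal SDs and rho of 0.3 to 0.9, the SE is understated by 19% down to 3%. Over the whole range examined (k of 0.8 to 1.25), the understatement runs from 29% to none. These figures rest on complete data and on assumed correlations and SD ratios; the effect in 11.3.1 is not quantified. The matter concerns how precisely secondary and additional results are reported. It should be corrected because the remedy is simple, but it does not touch the primary test or the stated power.

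**What to change.** 1. In all three sections, state that the null is zero mean change (or zero mean percent change) and that the target is the unconditional mean.
2. In 11.2.3 and 11.2.4, enter baseline as one of the repeated outcomes (baseline, 3, 6, 9 and 12 months), with visit as a factor, an unstructured covariance and no baseline covariate. Report each visit-minus-baseline contrast with a 95% CI. Name a fallback for non-convergence at small n: a simpler covariance structure or the unadjusted paired change.
3. Alternatively, keep the present models and use an unconditional SE that adds the baseline term: SE² = model SE² + b²·s_B²/n, where b is the slope of change on baseline and s_B the baseline SD.
4. In 11.3.1, drop the baseline covariate or use the unconditional SE. This keeps percent change as the quantity reported, in line with protocol 3.8.

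**Cost.** A few sentences of SAP text and changed model statements; no new data. Standard errors grow by the inverse of the ratio: about 3% to 24% with equal SDs (1/0.975 to 1/0.806), and 0% to 41% over the full range shown (1/1.00 to 1/0.709). Entering baseline as an outcome keeps the baseline information of women with missing later visits, which matters with 33% dropout expected by 12 months. The plain paired change, and 11.3.1 without the covariate, give up that use of baseline.

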11.2.4 St. Mark's (Vaizey) Incontinence Severity Score

The St. Mark's (Vaizey) Incontinence Severity questionnaire assesses seven aspects of incontinence severity (solid stool incontinence, liquid stool incontinence, gas incontinence, lifestyle alteration, the need to wear a pad or plug, taking constipating medicines, and lack of ability to defer defecation for 15 minutes).

An overall incontinence severity score, calculated and entered on the CRF, is derived as follows:

- The first 4 questions are scored on a 5-point scale, where 0=Never and 4=Daily
- The next 2 questions (wearing a pad or plug and taking constipating medicines) are scored where 0=No and 2=Yes
- The last question (deferring defecation) is scored where 0=No and 4=Yes
- The item scores are summed to create an overall score on a 24-point scale, where 0 is perfect continence and 24 is total incontinence.
- If any of the items used to create the overall score are missing, the score will be missing. (A missing FI bother item result will not affect the overall score).

An FI bother scale is also administered as part of this assessment. The amount that a subject's bowel control symptoms bothers her on the visit day is ranked on a 4-point scale, where 0=Not at all and 3=Greatly.

The severity score results, changes from baseline and/or percent changes from baseline may be summarized by visit. Changes from baseline in the severity score

will be analyzed using a repeated measures model with baseline severity score as a covariate. Least squares means and associated p-values may be presented for each timepoint during the Treatment Period.

The FI bother scale may be summarized by visit using the PP population. The change from baseline in the FI bother scale, which could take on values of -3 to 3 may also be summarized (continuously) and evaluated using the Wilcoxon Signed Rank test to determine if the average score is significantly different from zero (i.e., no change). The percent change from baseline in FI bother may be summarized as less bothersome (values <0), no change (0), or more bothersome (values >0) by visit.

The individual item scores, overall severity score, and FI bother scale may be listed by subject and visit.

11.3 Additional Analyses of Diary Data

11.3.1 FI Episodes

The average number of FI episodes per week for each subject may be summarized by diary period (Baseline, Test, 3 month, 6 month, 12 month). The change from baseline and percent change from baseline may also be summarized for each Treatment Diary (3 month, 6 month, 12 month).

Percent changes from baseline will be analyzed using a repeated measures model with baseline average number of weekly episodes as a covariate. Least squares means and associated p-values will be presented for each timepoint during the Treatment Period.

The percent change from baseline in FI episodes will be further categorized by degree of improvement (<50% reduction, >= 50% reduction, >75% reduction, and 100% reduction) and the percent of subjects in each category summarized for each Treatment Diary. These analyses will be based on the PP population.

11.4 Exploratory Analyses

No exploratory analyses are planned.

11.5 Subgroup Analyses

Subgroup analyses may be performed by FI phenotype, including but not limited to analyses of FI episodes, FIQOL, St. Mark's (Vaizey), and demgraphic comparisons.

12 SAFETY AND TOLERABILITY

12.1 Adverse Events

All adverse events (AEs) occurring after a subject has been fit with the Eclipse System, at the Initial Fitting Visit, will be recorded. All AEs will be coded into system organ class and preferred term using MedDRA v17.0.

The Clinical Events Committee (CEC) will review all AEs at regular intervals to confirm MedDRA classification and determine the relationship to the study device (not related, unlikely, probable, definite, or unknown). Where appropriate, relationship to the study device will be further classified by component (Eclipse insert, trial insert, sizer, pump, valve, extension tube, regulator). For a more detailed description of the AE review/adjudication and MedDRA coding processes, please refer to the CEC Charter ver. 2.0.

The incidence of adverse events will be summarized by system organ class and preferred term. Subjects will be counted at most one time per system organ class and at most one time per preferred term. For summaries by severity, subjects will be counted at most one time per system organ class and at most one time per preferred term, at the highest recorded severity.

The following summaries will be provided:

- AEs per time period (e.g. fitting vs. treatment)
- AEs related to study device (defined as those categorized by the CEC as being probably or definitely related to study device)
- Serious adverse events (SAEs; if applicable)
- AEs leading to withdrawal from the study
- AEs by severity
- AEs related to study device, by severity

An additional summary of TEAEs, by preferred term, sorted by descending overall frequency, will also be presented.

Data listings, including system organ class and preferred term, will be provided for all AEs, all SAEs, and all AEs related to study device.

Separate listings will be provided for all adjudicated events, and will include all information provided by the CEC.

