3.5 Endpoints

The primary effectiveness endpoint is the proportion of treatment responders at the 3 month time point in the ITT population.

Secondary effectiveness endpoints are:

- The proportion of responders at the 3, 6 and 12 month time points in the PP population.
- The change from baseline in mean scores on subject-reported outcomes related to symptoms and quality of life as reported by St. Mark's (Vaizey) Incontinence Severity Score, and FIQOL at the 3, 6, 9 and 12 month time points
- PGI-I scores at the 3, 6, 9 and 12-month time points

The safety endpoint is the safety of the device, as assessed by the number of device-related (Eclipse System) adverse events and device –related serious adverse events, as adjudicated by the Clinical Events Committee (CEC).

Subjects who are screen failures will not be included in the effectiveness endpoint analysis. However, their data will be reviewed to understand reasons for screen failure. All subjects in whom the device was inserted, even if just for fitting, will be included in the safety analysis. For all screen fail subjects, the Investigator or designee will complete Case Report Forms related to the completed visits and a Study Exit Form.

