3.10 Safety Analyses

The number of overall adverse events will be summarized using the Medical Dictionary for Regulatory Activities (MedDRA) system organ class and preferred term and listings will be reviewed at regular intervals by the CEC. Device-related adverse events, and device-related serious adverse events occurring at each time point will be summarized. The CEC adjudicated AEs will be utilized in the safety endpoint analyses

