6.5 Safety Measures

Safety will be assessed using device-related adverse events and device-related serious adverse events. Adverse events will be adjudicated by a Clinical Events Committee (CEC). Please reference the CEC Charter ver. 2.0 for a detailed description of the adverse event adjudication process.

Page 9 of 19

Confidential

¹ Richter, et al. non-surgical management of stress urinary incontinence: ambulatory treatments for leakage associated with stress (ATLAS) trial. Clinical Trials 2007; 4: 92-101.

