7.2 Analysis Populations

The Safety Population will include all subjects exposed to any part of the Eclipse System during or after Visit 2 (Initial Fitting Visit). This will include all subjects who

were unsuccessfully fitted, and screen failures. This will be the primary analysis population for all safety analyses.

The Test Population will include all subjects who are successfully fit with the Eclipse Insert and successfully completed a Test Diary.

The Intent-to-Treat (ITT) Population will include all subjects who are successfully fit with the Eclipse Insert, successfully complete Visit 4, and enter the Treatment Period.

The Per-Protocol (PP) Population include all subjects in the ITT population who complete Visit 5, complete at least 10 out of 14 consecutive days of diary data at the 3 month visit, and have no major protocol deviations.

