10 CHANGES IN CONDUCT OR PLANNED ANALYSES FROM THE PROTOCOL

This analysis plan was developed in conjunction with CA005 Protocol Revision D, dated 09 Feb 2017. No changes in conduct or planned analysis have occurred.

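### SAP 12.1 plans no device-related SAE summary, no event counts and no time-point split of device-related AEs, although the protocol makes these the safety endpoint

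*SAP*

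**What the plan says.** Protocol 3.5 assesses safety by "the number of device-related (Eclipse System) adverse events" and by device-related SAEs, both as adjudicated by the CEC. Protocol 3.10 adds: "Device-related adverse events, and device-related serious adverse events occurring at each time point will be summarized". SAP 6.5 keeps the same two measures: "Safety will be assessed using device-related adverse events and device-related serious adverse events".

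The summaries listed in SAP 12.1 are:
- AEs by period, given as "AEs per time period (e.g. fitting vs. treatment";
- AEs the CEC judged probably or definitely device-related;
- SAEs, if applicable;
- AEs leading to withdrawal;
- AEs by severity;
- device-related AEs by severity.

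A further table ranks preferred terms by frequency. There are listings of all AEs, all SAEs and device-related AEs, and separate listings of the adjudicated events. The counting rule is: "Subjects will be counted at most one time per system organ class and at most one time per preferred term".

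SAP 10, referring to Protocol Revision D, states: "No changes in conduct or planned analysis have occurred".

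On the population, SAP 7.2 defines the Safety Population as everyone exposed to any part of the system from Visit 2 on, including failed fits and screen failures, and says: "This will be the primary analysis population for all safety analyses". Protocol 3.3 has the same rule.

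**The concern.** The objective is durability of safety after 3 and 12 months (Protocol synopsis, SAP 5.1). The protocol's safety endpoint fits that objective, because it counts events of the right kind and follows them over time. The list in SAP 12.1 does not carry it through. A single treatment block, for AEs of any cause, cannot show whether device-related AEs fall, hold or rise between dispensing of the Eclipse Insert and month 12. Device-related SAEs, half of the endpoint, have no table of their own. The SAE line is also conditional, so a zero might not be reported at all.

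The second issue concerns the denominator. SAP 12.1 names none for the period split, so the default in SAP 7.2 would apply. Women who were fitted but never entered the Treatment Period cannot have a Treatment Period AE, yet they would be in the denominator and would pull the percentage down.

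**Working it through.** The documents state no figure for the safety summaries, so there is none to reproduce. The first part is a comparison of texts and the second is simple arithmetic.

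**1. Endpoint against planned tables**

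| Promised in Protocol 3.5 / 3.10 | Planned in SAP 12.1 |
|---|---|
| Number of device-related AEs | Subjects with device-related AEs, once per class and per term; no event count |
| Device-related AEs at each time point | Overall and by severity; no time split |
| Number of device-related SAEs | All SAEs, not split by relationship |
| Device-related SAEs at each time point | None |

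The one time split in SAP 12.1 is for all AEs. The statement of no change in SAP 10 is therefore inaccurate on this point.

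**2. Why intervals need the number still in the study**

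Protocol 3.11 expects 33% dropout between the start of the Treatment Period and month 12. With 150 treated, 150 x (1 - 0.33) = about 100 complete. At a constant event rate per woman, late intervals would show fewer events only because fewer women remain.

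**3. Size of the denominator effect, if the Safety Population is used**

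The ratio is (women entering the Treatment Period) / (women fitted). The reported percentage equals the percentage among treated women multiplied by this ratio.

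Inputs:
- Protocol 2.2: up to 625 screened for up to 150 treated.
- Protocol 3.11: 160 to 600 recruited for 40 to 150 treated.
- Protocol 2.6: before fitting, up to 25% lost on general or pelvic exam criteria and up to another 25% on baseline episode frequency.
- Protocol 1.6.2 (LIFE): 61 entered treatment; 117 in the Safety Cohort.

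The second 25% can be read as a share of all screened (0.50 remain) or of those left (0.75 x 0.75 = 0.5625 remain).

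| Screened | Treated | Fitted at 0.50 | Ratio | Fitted at 0.5625 | Ratio |
|---|---|---|---|---|---|
| 625 | 150 | 312.5 | 0.480 | 351.6 | 0.427 |
| 600 | 150 | 300 | 0.500 | 337.5 | 0.444 |
| 160 | 40 | 80 | 0.500 | 90 | 0.444 |

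LIFE: 61/117 = 0.521. (LIFE also had 61 women with device-related or possibly related AEs. That is a different group with the same count, and it is not used here.)

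The range is 0.43 to 0.52. As an illustration, suppose 20% of treated women had a Treatment Period AE (an assumed value): 30 of 150. Over 351.6 fitted this reads 8.5%, over 300 it reads 10.0%, and at the LIFE ratio it reads 10.4%.

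**The case against.** The best defence is that most of the material is there. Device-related AEs are summarised overall and by severity, all SAEs are summarised, and the listings include adjudicated events with all CEC information, so a device-related SAE could be found. LIFE had two SAEs in total and none device-related. With similar numbers, a reader could work out the result from the SAE table and the listing. No hypothesis test or success criterion depends on these tables. All of that is true. A reader might infer that the SAP drops the safety endpoint altogether, and the documents do not support that. What stands is narrower: a listing is not the summary that the protocol promises, and three specific summaries are missing.

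The period split is introduced with an e.g., so more than two periods are allowed, and Protocol 3.10 does not spell out its time points. Months 3, 6, 9 and 12 are a reading based on the visit schedule, where AEs are reviewed at each of those visits. But the open wording still covers AEs of any cause and commits to no split of the device-related ones.

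A reader might also infer that no denominator is stated. One is stated by default, in SAP 7.2 and Protocol 3.3. The criticism is that this default suits fitting-period and overall summaries but not Treatment Period rows. Since the protocol has the same rule, changing it is a departure from the protocol that must be recorded.

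Finally, a reader might use LIFE's 93 events in 61 subjects to say how many events subject counting would hide. The documents do not allow that. A woman with two different terms appears in both term rows, LIFE is not broken down by term, and LIFE included possibly related events while SAP 12.1 uses probable and definite.

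**Conclusion.** The point holds on the texts. SAP 12.1 lacks a device-related SAE summary, counts of device-related events, and any time-point split of device-related AEs. Protocol 3.5 and 3.10 promise these, and SAP 10 records no change. Tables made only as listed would not answer the durability-of-safety objective.

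The denominator issue is secondary and conditional. If the Safety Population is used for the period split, Treatment Period percentages would read at about 0.43 to 0.52 of their value among treated women. This rests on the planned yield, on pre-fitting losses at their stated upper limits, and on LIFE as a cross-check. At the same yield, smaller pre-fitting losses would mean more women fitted and a lower ratio; other losses before fitting would raise it. It is a consequence of the default as written, not proof that the tables will be built that way.

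The effectiveness conclusion is unaffected. The SAP should be corrected before database lock, so that the form of the safety summaries is not chosen after the data are seen.

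**What to change.** 1. **SAP 12.1, added summaries.** Add CEC-adjudicated device-related AEs and device-related SAEs, each as number of events and number of subjects, for the fitting period and for each Treatment Period visit interval (to 3, 6, 9 and 12 months). Show the number of women in the study at the start of each interval, and report zeros.
2. **Denominator.** Use women who entered the Treatment Period (the ITT population) for Treatment Period rows. Keep the Safety Population for fitting-period and overall summaries. State the exception in SAP 7.2.
3. **Period assignment.** Assign each AE by its onset date relative to dispensing of the Eclipse Insert at Visit 4. AEs in screen failures then all fall in the fitting period.
4. **SAP 10.** Correct the statement of no change, and record the denominator exception to Protocol 3.3.

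The cost is SAP wording and some table rows. No new data are needed if the AE form records onset date, which is assumed because the form is not in the documents. The downsides are small counts in the interval rows and a possibly less favourable Treatment Period AE percentage.
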